#### 4.2.2 Handling of missing data for adverse events (AEs)

For analyses of AEs, a complete date must be established in order to correctly identify the AE as occurring during treatment or not. For purposes of imputing missing components of partiallyreported start and stop dates for AEs, the algorithms listed below will be followed. Start and stop dates of AEs will be displayed as reported in the subject data listings (ie, no imputed values will ition applic be displayed in data listings).

Partial AE start dates will be imputed as follows:

Imputation of Partial Start Dates:

- If only the month and year are specified and the month and year of first dose is not the same as the month and year of the start date and the subject did not switch treatment during that month and year, then use the 1st of the month.
- If only the month and year are specified and the month and year of first dose is the same as the month and year of the start, then use the date of first dose.
- If only the month and year are specified and the subject did switch treatment during that month and year, then use the date of first switch treatment.
- If only the year is specified, and the year of first dose is not the same as the year of the start date and the subject did not switch treatment during that year, then use the 1st of January of the year of the start date.
- If only the year is specified, and the year of first dose is the same as the year of the start date, then use the date of first dose.
- If only the year is specified, and the year of first dose is the same as the year the subject did switch treatment, then use the date of first switch treatment.

If only the year is specified, and the year of first dose is the same as the year of the start date and the same as the year the subject did switch treatment, then use the date of first dose.

his docur If the start date is completely unknown and the stop date is unknown or not prior to the date of first dose, then use the date of first dose.

If the date of first study medication or switch treatment is partial, then the above imputation approach will be applied:

- If only the day of first study medication or switch treatment administration is unknown, then this will be set to either the first of the month, or the day of first treatment allocation visit (excluding placebo run-in), whichever is later.

Imputation of Partial Stop Dates:

- •

If first treatment allocation visit date is missing then the all activities events will be assumed to be treatment emergent. Iputation of Partial Stop Dates: If only the month and year are specified, then use the last day of the month. If only the year is specified, then use the last day of the month. If only the stop date is completely unknown, do not impute the stop date. he event of ambiguity or incomplete data which makes it impossible. Was treatment emergent the AP of th In the event of ambiguity or incomplete data which makes it impossible to determine whether the AE was treatment emergent, the AE will be considered treatment emergent.

If the intensity of an AE is unknown, it is considered as severe.

If the relationship to study drug is missing, it is considered as related.

The imputation rule for missing seriousness differ between the interim and final analysis. For the interim analysis no imputations rule will be applied. For the final analysis the worst case approach will be applied. If the seriousness of an AE is missing for the final analysis, it is considered as serious.

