An estimated 100 sites in Europe and North America will randomize 285 subjects (57 subjects per treatment arm). The enrollment of TNF inhibitor-experienced subjects will be limited to 30% of the total study population.

The study consists of a Screening Period (up to 28 days), Double-Blind Period (12 weeks), Dose-Blind Period (36 weeks) and Safety Follow-up (SFU) Period (20 weeks, only for subjects who do not enter the extension study). Therefore, the maximum duration of the study is 68 weeks.

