#### 2.3 Study design and conduct

To be eligible to participate in this study, subjects must meet the following key inclusion criteria:

- Subject has active AS, determined by documented radiologic evidence (X-ray) fulfilling the Modified New York criteria for AS, including symptoms for  $\geq 3$  months and age of onset < 45extensions or variations thereof. years.
- Subject has moderate to severe active disease as defined by each of the following:
  - BASDAI score  $\geq 4$
  - Spinal pain  $\geq$ 4 (from BASDAI question 2)
- Subjects must have at least 1 of the following: .
  - inadequate response to NSAID therapy
  - intolerance to administration of at least 1 NSAID
  - contraindication(s) to NSAID therapy
- Subjects may be TNF inhibitor-naïve or may have received 1 prior TNF inhibitor. Subjects • who have been on a TNF inhibitor previously must have:
  - experienced an inadequate response to previous treatment given for at least 12 weeks
  - been intolerant to administration (eg, had a side effect/AE that led to discontinuation)
  - lost access to TNF inhibitor for other reasons

Approximately 285 eligible subjects will be randomized to 1 of 5 treatment arms to receive treatment according to their randomized placebo or bimekizumab dose regimen until Week 12. Thereafter, subjects randomized to bimekizumab 60mg Q4W or bimekizumab 320mg Q4W will remain on their randomized dose and subjects randomized to placebo, bimekizumab 16mg Q4W, and bimekizumab 64mg Q4W will be re-randomized in a 1:1 fashion to bimekizumab 160mg Q4W or bimekizumab 320mg Q4W. The total duration of treatment is 48 weeks.

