The incidence of TEAEs will be summarized by MedDRA SOC, high level term, and PT. Tables with incidences of classified TEAEs by maximum intensity, by relationship, and by subject number will be provided. The incidence of non TEAEs, non-serious TEAEs above the reporting tions thereof threshold of 5% of subjects and relationship will be summarized. Furthermore the incidence of all TEAEs, serious TEAEs, non-serious TEAEs, and TEAEs leading to study discontinuation and/or permanent withdrawal of study medication, adverse drug reactions, fungal infectious disorder TEAEs, opportunistic infection (including tuberculosis) TEAEs, malignant or unspecified tumor TEAEs, malignant tumor TEAEs, major cardiovascular event TEAEs, haematopoietic cytopenias TEAEs, neuropsychiatric events TEAEs, inflammatory bowel disease TEAEs, hypersensitivity and anaphylactic Reaction TEAEs, hepatic events TEAEs, and TEAEs by timing of onset relative to AbAb Status will be summarized. In addition, an overall summary table will be provided.

The tables will be split into the Double-Blind Period and the complete treatment period (exception non TEAE table and TEAEs by timing of onset relative to AbAb Status). Presentations for the Double-Blind Period will summarize AEs that start prior to or at Visit 7 (see details given above) by treatment group as randomized for the Double-Blind Period. Presentations for the complete treatment period will only summarize AEs that occur under treatment with bimekizumab, irrespective of the treatment period. For summaries of the bimekizumab 160mg, and bimekizumab 320mg treatment groups, patients randomized to Placebo, bimekizumab 16mg or 64mg at Baseline will only be included with AEs that start in the Dose-Blind Period. The all bimekizumab treatment group will also present AEs occurring under bimekizumab 16mg or 64mg treatment in the Double Blind Period. AEs for each subject will be summarized based on the treatment actually received at the onset of each particular AE.

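### The sixth start-date rule for adverse events leaves out the event's own year, so it conflicts with the fourth rule and leaves one year pattern with no imputed date

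*SAP*

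**What the plan says.** Section 4.2.2 lists start-date rules as bullets. The fourth to seventh deal with a start date of which only the year is known:

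- **Fourth:** the first-dose year "is not the same as the year of the start date and the subject did not switch treatment during that year". The imputed date is 1 January of the start year.
- **Fifth:** "the year of first dose is the same as the year of the start date, then use the date of first dose".
- **Sixth:** "the year of first dose is the same as the year the subject did switch treatment, then use the date of first switch treatment".
- **Seventh:** the first-dose year equals the start year "and the same as the year the subject did switch treatment, then use the date of first dose".

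The fourth, fifth and seventh rules refer to the start year; the sixth does not. The corresponding rule for dates with month and year does tie the switch to the event's own month: "If only the month and year are specified and the subject did switch treatment during that month and year". No precedence among the rules is stated. Section 4.2.3 repeats the same four rules for medications and adds one for a year-only start with an end date before first dose.

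The imputed date matters because, under Section 10.2, "AEs for each subject will be summarized based on the treatment actually received at the onset of each particular AE". Section 10.2 also assigns an event on the day of the switch (Visit 7, Week 12) to the Double-Blind treatment, except adverse drug reactions and hypersensitivity or anaphylactic reactions, which go to the Dose-Blind treatment.

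**The concern.** A switch rule for a year-only date should ask whether the switch fell in the year of the event. The sixth rule asks instead whether the switch fell in the year of first dose. This looks like a drafting slip, since the month-and-year counterpart is worded correctly. It has two consequences.

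1. When first dose and switch share a year and the event is in a different year, the fourth and sixth rules both apply and give different dates.
2. When the switch falls in the year after first dose and the event is in that later year, no rule applies. The fourth is blocked by its no-switch condition, and the other three fail because the first-dose year matches neither the event year nor the switch year.

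At stake is whether an event is counted under placebo or a low dose, or under bimekizumab 160mg or 320mg, and in one pattern whether it is treatment-emergent at all. Onset dates also enter the exposure-adjusted incidence rates of Section 10.2.2.

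**Working it through.** The SAP gives no figure to reproduce here. The check applies the four rules literally to each pattern of years.

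**Inputs.** Let first dose fall in year Y. The switch is absent (160mg and 320mg arms), in Y, or in Y+1, because it comes after 12 weeks, or 84 days (Section 2). The event year runs from Y−1 to Y+2. That makes 3 × 4 = 12 patterns.

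| Switch | Event year | Rules that apply, as written | Result as written | After rewording |
|---|---|---|---|---|
| none | Y−1 | 4th: 1 Jan | one date | 1 Jan |
| none | Y | 5th: first dose | one date | first dose |
| none | Y+1 | 4th: 1 Jan | one date | 1 Jan |
| none | Y+2 | 4th: 1 Jan | one date | 1 Jan |
| Y | Y−1 | 4th: 1 Jan; 6th: switch | conflict | 1 Jan |
| Y | Y | 5th and 7th: first dose; 6th: switch | settled by 7th | first dose |
| Y | Y+1 | 4th: 1 Jan; 6th: switch | conflict | 1 Jan |
| Y | Y+2 | 4th: 1 Jan; 6th: switch | conflict | 1 Jan |
| Y+1 | Y−1 | 4th: 1 Jan | one date | 1 Jan |
| Y+1 | Y | 5th: first dose | one date | first dose |
| Y+1 | Y+1 | none | **no date** | switch |
| Y+1 | Y+2 | 4th: 1 Jan | one date | 1 Jan |

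As written, seven patterns give one date and an eighth is settled by the seventh rule. Three are in unresolved conflict and one has no rule: 7 + 1 + 3 + 1 = 12. After the rewording all 12 give one date.

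**What the conflicts do.**

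- *Event in Y−1.* Events are recorded from consent (Section 10.2) and screening lasts up to 28 days, so this needs a first dose early in the year. The fourth rule makes the event non-treatment-emergent. The sixth makes it treatment-emergent at the switch.
- *Event in Y+1.* Treatment lasts 48 weeks, or 336 days. Since 365 − 336 = 29, a first dose after about the end of January leaves treatment running into Y+1. The fourth rule gives 1 January of Y+1, in the Dose-Blind Period. The sixth gives the switch day, which Section 10.2 generally assigns to the Double-Blind treatment. An event on 160mg or 320mg could then be counted under placebo, 16mg or 64mg.
- *Event in Y+2.* This is included for completeness. It lies at the far end of follow-up and matters little.

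**How often the uncovered pattern could arise.** Only the placebo, 16mg and 64mg arms switch: by Section 2.3 those up to "bimekizumab 64mg Q4W will be re-randomized in a 1:1 fashion". That is 3 of 5 arms, or 285 × 3/5 = 171 subjects. The switch falls in the next year when first dose is in the last 84 days of a year. If enrolment were uniform over the year, which the SAP does not state, this is 84/365 = 23% of switching subjects. That is 171 × 84/365 ≈ 39 subjects, or about 14% of 285. Only those among them with a year-only event date in the switch year are affected.

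**Medications (Section 4.2.3).** Under Section 6.4, a medication with a stop date missing, or on or after first dose, is concomitant whatever start date is imputed. If it ended before first dose, the added end-date rule gives 1 January of the start year, hence prior. But if its start year is also the first-dose year, the fifth rule gives the first-dose date. That conflict remains after the sixth rule is reworded.

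**The case against.** The strongest reply is that Section 4.2.2 sets out to fill in missing parts of a date. In a year-only date the year is known, so applying the sixth rule to an event in another year would overwrite recorded data. The fourth rule fits those cases exactly, and a sensible programmer would use it. This makes the wrong date less likely. It does not remove the conflict, because the sixth rule's conditions are met and no precedence is stated, and it does nothing for the pattern without a rule.

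A second reply is that Section 4.2.2 counts an event as treatment-emergent where the data leave this unclear. That settles emergence only. In the uncovered pattern every date in the event year is after first dose, so the open question there is which treatment the subject was on.

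Four broader readings are tempting, and the SAP does not support them:

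- *That the year-only rules as a set ignore the event year.* Only the sixth does.
- *That the case with all three years equal is an open conflict.* The seventh rule is written for it, and it agrees with the fifth.
- *That anyone whose Double-Blind Period crosses 31 December has no rule.* Subjects on 160mg or 320mg do not switch, and the fourth rule covers their later-year events.
- *That medications are widely misclassified.* The end-date rule in Section 4.2.3 and the definitions in Section 6.4 largely prevent this.

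**Conclusion.** The point holds in limited form. The sixth rule of Section 4.2.2 is misworded. It conflicts with the fourth rule whenever first dose and switch share a year that is not the event's, and one realistic pattern in the three switching arms has no rule. Two programmers following the text could attribute the same event to different treatments.

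The effect on adverse event rates is probably small. That judgement rests on the assumption that year-only onset dates are rare in a monitored trial; the SAP gives no frequency. The figure of about 39 subjects is an upper bound on those exposed to the gap under uniform enrolment, not an estimate of events affected. Nothing here touches the primary or secondary efficacy analyses.

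**What to change.** In Section 4.2.2, replace the sixth start-date rule with wording to this effect: *Year-only start date: where the start year equals the year of the treatment switch but differs from the first-dose year, impute the date of the first switch.* Every pattern in the table then gives one date.

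Make the same edit in Section 4.2.3 for consistency. Add there that the rule for an end date before first dose takes precedence over the rules that give the first-dose date (the fifth, and the seventh where it repeats the fifth). Without that sentence the two would still conflict.

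The cost is one bullet in each of two sections, one sentence on precedence, and a check that the programs match. No new data are needed.

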- If the start date is completely unknown and the stop date is prior to the date of first dose, then set the start date to the 1st of January of the year of the end date.

If the date of first study medication or switch treatment is partial, then the below imputation approach will be applied:

- If only the day of first study medication or switch treatment administration is unknown, then this will be set to either the first of the month, or the day of first treatment allocation visit (excluding placebo run-in), whichever is later.
- If both the day and month of first study medication or switch treatment are unknown, then this date will be imputed to be the date of first treatment allocation visit.

Imputation of Partial Stop Dates:

- If only the month and year are specified, then use the last day of the month.
- If only the year is specified, then use December 31st of that year.
- If the stop date is completely unknown, do not impute the stop date.

There will be no imputation of any other missing data.

#### 4.3 Interim analyses and data monitoring

Two interim analyses are planned for the study after the subjects have completed 12 and 48 weeks.

### Miterim analysis Week 12 4.3.1

After all enrolled subjects have completed the 12 weeks Double-Blind Period, an interim analysis will be performed (i) to analyze the dose:exposure response for the ASAS40 response criteria to determine the optimal therapeutic dose(s) for subsequent studies, and (ii) to perform a comprehensive evaluation of all Double-Blind data of the study.

No separate SAP for the interim analysis will be provided. The interim analysis is a limited version of the final analysis and will focus on the primary and secondary efficacy analysis and comprise the results of the 12 weeks Double-Blind Period. The TFL shells for the interim and final analysis will be provided in two different documents.

The interim analysis will summarize disposition, demographics, AS history, Baseline characteristics, AS concomitant medication, efficacy analysis, AEs and treatment-emergent AEs (derivation Section 10.2), hematology and biochemistry laboratory data, and Electronic

Longy, biochemistry Line ustings. For the interim analysis only selected Line ustings. For the interim analysis only selected Line ustings will be provided as listed in Table 12–3. For efficacy the interim analysis will include following primary and secondary variables: ASAS40,20,5/6 response at Week 12, and change from Baseline in BASDAI, ASDAS-CRP, BASFI at Week 12. The variables will be analyzed using the same methods described in Section 8.1.2 and Section 8.2 including supportive and sensitivity analyzed (f Section 8.1.4). In addition, summary tables for the prime the ASAS components will be provided for the prime the ASAS components will be provided for the prime frequency tables be frequency tables by each visit. Continuous variables will be summarized using descriptive statistics by each visit. Time to onset of ASAS20 response and ASAS40 response will be summarized and plotted as described in Section 8.3.

PK and PD data will be analyzed in the interim analysis as described in Section 9.1 and Section 9.2. PKPD will be analyzed as part of the exposure:response modeling outside of the scope of the SAP. Biomarker data will not be analyzed in the interim analysis.

The interim analysis includes selected data up to Week 12 and in addition data up to Week 16. The data up to Week 16 may include partial results up to the time the database for Week 12 was locked for ongoing subjects. All analyses for the period between Week 12 and Week 24 are only for those treatment groups that are not rerandomized. Following variables will be analyzed: ASAS40, ASAS20, ASDAS-CRP, BASDAI, PK, AbAb and TEAEs. It depends on the analysis how those additional time points will be presented in the interim analysis. Two summary tables for TEAE will be presented. The first table will include TEAEs with a relative TEAE start date less equal 84 (12\*7) days by treatment group at Baseline. The second table will include TEAEs with a relative TEAE start date less equal 112 (16\*7) days by the following treatment groups: bimekizumab 160mg and bimekizumab 320mg. The summary table for the other variables will present only data up to Week 12 for the Baseline treatment groups Placebo, bimekizumab 16mg, and bimekizumab 64mg. Data up to Week 16 will be presented for bimekizumab 160mg and bimekizumab 320mg All Listings which include data up to Week 16 will use the same approach.

If an AE occurs on the same day as the treatment switch (Visit 7, Week 12) then the AE will be allocated to the Double-Blind treatment. An exception from this general rule is made for adverse drug reactions (ADRs), and AE of hypersensitivity reactions and anaphylactic reactions. If those AEs occur on the same days as the treatment switch, the AEs will be allocated to the Dose-Blind treatment and will not be presented for the interim analysis.

Exposure of study medication will not be summarized but a listing will be provided including following information: date of first dose, date of last dose, and duration of exposure. The last dose for the Double-Blind Period is planned on Visit 6 (Week 8).

This docut For the interim analysis, the database will be locked and the treatment codes will be made available to UCB personnel with exception of operational staff working on the study. An interim report will be written. The investigators and subjects will remain blind to the assigned

bimekizumab dosing regimen until the subject completes the Dose-Blind Period at Week 48. Further details are available in the AS0008 blinding plan.

itations thereof Safety data will be provided to an independent Data Monitoring Committee (DMC). The DMC will review those safety data periodically. The composition and operation of the DMC will be defined in the DMC charter. The presentation and analysis of data for the DMC meetings is described within a separate DMC SAP.

#### 4.3.1.1 Changes from interim analysis Week 12 to SAP-defined analyses

For TEAE two summary tables were presented as described in previous section with one modification: the first table was displaying all TEAE during the Double-Blind Period instead of limiting it TEAE with a relative TEAE start date less equal 84 days.

The definitions of AE of special monitoring were updated with the third SAP Amendment after the interim analysis. The interim analysis used the previous definition which is displayed in Section 4.3.1.2. The interim analysis only displayed the overall number of AE of special monitoring by treatment group.

The baseline definition for CRP and hs-CRP measurements were updated with the fifth SAP Amendment after the interim analysis. The interim analysis used the previous definition: The last valid measurement before first dose of study drug (Visit 2) will be used as the Baseline value.

### Search and selection criteria for AE of special monitoring for interim 4.3.1.2 analysis Week 12

Following AEs are defined as TEAEs of special monitoring:

- Fungal infectious disorder •
- Opportunistic infection (including TB)
- Malignant or unspecified tumor
- Malignant tumor
- Major cardiovascular event
- Haematopoietic cytopenias
- Neuropsychiatric events
- Inflammatory bowel disease
- Hypersensitivity and anaphylactic reaction
- Hepatic events

## Fundal Infectious disorder

All TEAEs which code into the High Level Group Term (HLGT) of "Fungal infectious" disorders" are classified as fungal infectious disorder.

